2.3 Study Duration

- **Screening Phase:** up to 6 weeks
- **Treatment Phase:** 48 weeks ± allowed windows (up to 48 treatments every week (±3 days)).
- **Follow-up Phase:**
 - Virologic Failure: until viral suppression is achieved. Additionally, subjects who experience virologic failure will return to clinic for long-term follow-up at 6 months and at one year from the time of the Virologic Failure Visit.
 - Non-Virologic Failure (NVF): 4 weeks

Total Study Duration will be 58 weeks, which does not include additional follow-up time for virologic failure subjects.

2.4 Study Treatments

2.4.1 Treatment Groups

Group	Study Drug	Dosage Form	IP concentration	Dosing Frequency and Amount	Route of Administration
A	PRO 140 350mg	Parenteral solution	175 mg/mL	2 injections of PRO 140 (2 X 1 mL/inj.) for 48 weeks	SC injection
B	PRO 140 525mg	Parenteral solution	175 mg/mL	2 injections of PRO 140 (2 X 1.5 mL/inj.) for 48 weeks	SC injection
C	PRO 140 700mg	Parenteral solution	175 mg/mL	2 injections of PRO 140 (2 X 2 mL/inj.) for 48 weeks	SC injection

3. STUDY OUTCOME MEASURES

3.1 Primary Outcome Measures

The following outcome measures will be assessed for all subjects and within each treatment group for PRO 140 350mg, 525mg and 700mg dose.

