5. RANDOMIZATION AND BLINDING

There were no blinding requirements planned for this study.

The first ~150 eligible subjects were enrolled to receive PRO 140 350mg SC weekly injection in a single-arm study. Subsequently, next ~150 subjects were randomized 1:1 to PRO 140 350mg (Group A) or PRO 140 525mg (Group B). An additional ~200 subjects will be randomized 1:1 to PRO 140 525mg (Group B) or PRO 140 700mg (Group C).

➤ For the first ~150 enrolled subjects:

- **Part 1:** 48-week, single-arm, open-label treatment phase
 - PRO 140 350mg SC weekly injection (Group A)

- **For the subsequent ~150 enrolled subjects:**
 - **Part 1:** 48-week, randomized, two-arm, open-label treatment phase
 - PRO 140 350mg SC weekly injection (Group A)
 - PRO 140 525mg SC weekly injection (Group B)
- **For the subsequent ~200 enrolled subjects:**
 - **Part 1:** 48-week, randomized, two-arm, open-label treatment phase
 - PRO 140 525mg SC weekly injection (Group B)
 - PRO 140 700mg SC weekly injection (Group C)

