6. ANALYSIS POPULATIONS

6.1 Intent-to-Treat Population

The Intent-to-Treat (ITT) population is defined as the set of subjects who were enrolled or randomized and have at least one dose of PRO 140.

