8.1.3 Demographics and Baseline Characteristics

Demographics and baseline characteristics (i.e., Age, Gender, Time since HIV diagnosis, Viral load at Screening Visit, etc.) will be summarized using appropriate descriptive statistics.

Medical history of the subjects will also be summarized and also provided as a by-subject listing.

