8.2.1.1 Adverse Events

Adverse events will be coded using Medical Dictionary for Regulatory Activities (MedDRA). TEAEs are defined as events with an onset on or after the first treatment. TEAEs will be summarized by treatment group, System Organ Class (SOC), and preferred term (PT). The following TEAE summaries will be provided:

- Overall (*i.e.*, regardless of severity or relationship to treatment)
- By severity grade (mild, moderate, severe, life threatening or death for SAEs)
- By relationship to study treatment (definitely related, probably related, possibly related, remotely related or unrelated)

In addition, separate summaries of SAEs, and AEs resulting in discontinuation of study treatment will be presented.

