8.2.2.1 Proportion of participants experiencing virologic failure at the assigned dose

The percentages of subjects with virologic failure (as defined in [Section 7.5.6](#)) will be presented descriptively by treatment groups for the ITT and PP populations.

Note: Assigned dose refers to the dose allocated at the time of randomization/enrollment.

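### The SAP's by-dose summaries pool three successive enrolment cohorts, so no planned summary shows either of the trial's concurrent randomised comparisons

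*SAP*

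**What the plan says.** SAP 2.4.1 defines Groups A, B and C by dose alone (350, 525 and 700 mg), and SAP 3.1 reports on that basis: "The following outcome measures will be assessed for all subjects and within each treatment group for PRO 140 350mg, 525mg and 700mg dose". Virologic failure (SAP 8.2.2.1) "will be presented descriptively by treatment groups for the ITT and PP populations". Time to failure (8.2.2.2), 24/48-week suppression below 50 copies/mL (8.2.2.8) and TEAEs (8.2.1.1) are also summarised by treatment group. Baseline characteristics (8.1.3) name no grouping.

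SAP 5 describes three successive cohorts. Of cohort 1 it says: "The first ~150 eligible subjects were enrolled to receive PRO 140 350mg SC weekly injection in a single-arm study". Cohort 2 (about 150) was randomised 1:1 to 350 or 525 mg, and cohort 3 (about 200) is to be randomised 1:1 to 525 or 700 mg. The ITT population is "the set of subjects who were enrolled or randomized and have at least one dose of PRO 140", so it takes in randomised and non-randomised subjects alike.

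No SAP section uses cohort, enrolment period or randomised status as a split. Protocol 8.6.3 plans no covariate analysis beyond the baseline value of the dependent variable. SAP 9.2 gives table headings only, so this reading rests on the text available. SAP 7.3 and 7.4 state that no inferential statistics are planned.

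**The concern.** Dose and enrolment period are entangled across the three columns. The earliest subjects all received 350 mg and only the latest could receive 700 mg. If risk changed between periods, a pooled table would show that change as a dose difference or hide a real one.

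The trial randomised twice, but the planned tables display neither comparison on its own. A reader also cannot tell from the tables that 350 vs 700 mg has no concurrent randomised comparison behind it.

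With no inference planned, the descriptive columns are the only evidence on dose that the SAP produces. That readers will compare them is an inference, but a reasonable one: Protocol 1.5 names inadequate dosing as the likely cause of rebound at 350 mg and expects better trough coverage at 525 and 700 mg.

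The documents do not say whether risk changed over time. Protocol 8.4 says everyone enrolled under the current version is randomised, which implies that the single-arm subjects entered under another version. What else differed between versions is not stated.

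**Working it through.** **Column sizes (SAP 5).** The 1:1 splits give 75 + 75 in cohort 2 and 100 + 100 in cohort 3.

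- A (350 mg): 150 + 75 = 225, of which 150/225 = 66.7% single-arm
- B (525 mg): 75 + 100 = 175, of which 42.9% from cohort 2 and 57.1% from cohort 3
- C (700 mg): 100, all cohort 3
- Total: 225 + 175 + 100 = 500

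This matches the approximately 500 subjects, with 100 at 700 mg, in SAP 4.

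**Artefact of pooling.** With no dose effect and cohort failure risks f1, f2, f3:

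- A − B = (2/3)(f1 − f2) + (4/7)(f2 − f3)
- B − C = (3/7)(f2 − f3)

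The documents give no cohort risks, so assume an equal fall of d points per cohort (p, p − d, p − 2d):

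- A = p − (75/225)d = p − 0.333d
- B = p − ((75×1 + 100×2)/175)d = p − 1.571d
- C = p − 2d
- Differences: A − B = 1.238d, B − C = 0.429d, A − C = 1.667d

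For example, 60/50/40% gives columns of 56.7%, 44.3% and 40.0% with no dose effect at all. A rising risk reverses the signs; no change gives zero.

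**Precision cost of splitting.** SE = 100·√[q(1 − q)(1/n1 + 1/n2)], with an assumed failure proportion q = 0.40:

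| Contrast | n | SE | 95% half-width (1.96·SE) |
|---|---|---|---|
| A − B, cohort 2 | 75, 75 | 8.00 | 15.7 |
| A − B, pooled | 225, 175 | 4.94 | 9.7 |
| B − C, cohort 3 | 100, 100 | 6.93 | 13.6 |
| B − C, pooled | 175, 100 | 6.14 | 12.0 |

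Over q = 0.30–0.50 the half-widths run 14.7–16.0 against 9.1–9.9 for A − B, and 12.7–13.9 against 11.3–12.3 for B − C.

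**Which view is closer to the truth.** Pooled root-mean-square error = √(SE² + bias²). The within-cohort contrasts carry no period bias.

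| d (points per cohort) | A − B within / pooled | B − C within / pooled |
|---|---|---|
| 0 | 8.0 / 4.9 | 6.9 / 6.1 |
| 5 | 8.0 / 7.9 | 6.9 / 6.5 |
| 10 | 8.0 / 13.3 | 6.9 / 7.5 |

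Break-even d = √(SE²within − SE²pooled) / coefficient:

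- A − B: √(64.0 − 24.4)/1.238 = 5.1
- B − C: √(48.0 − 37.7)/0.429 = 7.5
- Over q = 0.30–0.50: 4.8–5.2 and 7.0–7.6

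**Alternative allocation.** Protocol 4 (Study Schedule) says instead that the first 300 subjects were all randomised 1:1 to 350 or 525 mg. With about 200 more, A = 150, B = 150 + 100 = 250 and C = 100, with no single-arm subjects. One change of d between the two periods still gives A − B = (100/250)d = 0.4d, B − C = 0.6d and A − C = 1.0d.

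**The case against.** The strongest reply is that nothing planned is invalidated. The SAP tests nothing, no stated objective compares doses, and each column is a valid description of the subjects assigned that dose. SAP 2.2 and 5 already disclose the enrolment sequence. All of that is true and it limits the harm. But disclosing the design in a methods section does not put the randomised comparisons into the tables, and the by-subject listings are not said to identify the cohort.

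A second reply is that pooling is often more accurate. At d = 5 it is still no worse for either contrast, and at d = 10 the split gains only 0.6 points for 525 vs 700 mg. This stands. It is the reason for showing both views instead of replacing one with the other.

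Third, equal steps are only one pattern of change. If risk changes only between cohorts 1 and 2, the A − B break-even is 6.29/0.667 = 9.4 points; if only between cohorts 2 and 3, it is 6.29/0.571 = 11.0. But d is a per-step figure: 5.1 per step is about 10.2 points across two steps, so the total change needed is similar.

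Fourth, the magnitude was worked out only for the failure proportion, and splitting TEAEs by System Organ Class and preferred term adds bulk. That is a fair point about table volume. Finally, Protocol 8.4 may be carried-over text, since 8.3 still says 300 subjects. That weakens it as evidence about versions but leaves SAP 5 untouched.

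**Conclusion.** The point holds. On the SAP's own account, the 350 mg column is about two-thirds non-randomised and the 525 mg column spans two periods. Neither concurrent randomised comparison is specified in any planned summary. The harm is to descriptive interpretation only, and its size is unknown because the documents give no cohort-specific risks. The coefficients 1.24, 0.43 and 1.67 per point of shift assume equal steps and no dose effect; the precision figures assume about 40% failure, with 30–50% shown.

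Splitting by cohort removes the period artefact for 350 vs 525 mg and 525 vs 700 mg, but cannot do so for 350 vs 700 mg. The change should be made: it is cheap and makes the trial's own randomisation visible. Confidence is medium, because the table layouts are not shown and the size of any shift is not known.

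**What to change.** Keep the by-dose columns and add, beside them, a breakdown by enrolment cohort (cohort 1: A; cohort 2: A and B; cohort 3: B and C) for:

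- baseline characteristics (SAP 8.1.3), the direct check on whether the patients changed between periods
- virologic failure and time to failure (8.2.2.1–8.2.2.2)
- 24/48-week HIV-1 RNA below 50 copies/mL (8.2.2.8)
- TEAEs and SAEs (8.2.1.1)

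Label the pooled columns as combining enrolment periods and, for 350 mg, randomised and non-randomised subjects. State that 350 vs 700 mg is not a randomised comparison. Descriptive intervals are optional. The rescue and re-suppression subsets (8.2.2.3–8.2.2.7) need not be split.

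So that cohort membership is unambiguous, reconcile Protocol 4 (first 300 all randomised) with the Protocol Synopsis, Protocol 3 and SAP 2.2 and 5 (first 150 single-arm).

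The cost is SAP wording and extra table columns from data already collected, with no added inference. The cohort cells are small (about 150, 75, 75, 100 and 100), so the within-cohort contrasts will be less precise than the pooled ones.

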3.1.1 Safety Outcome Measures

The following metrics will be analyzed to assess the clinical safety of PRO 140 monotherapy regimen:

- Incidence of Treatment-Emergent Adverse Events (TEAE)
- Incidence of Treatment-Emergent Serious Adverse Events
- Incidence of Injection Site Reactions by Investigator evaluation
- Frequency of Grade 3 or 4 adverse events as defined by the DAIDS Adverse Event scale
- Tolerability of repeated subcutaneous administration of PRO 140 as assessed by study participants (using Visual Analogue Scale)
- Changes and shifts in laboratory measurements over time
- Changes in vital signs and weight over time
- Changes and shift in Electrocardiogram (ECG) parameters over time
- Incidence of Physical Examination abnormalities over time

3.1.2 Efficacy Outcome Measures

- Proportion of participants experiencing virologic failure at the assigned dose

Note: (1) Virologic failure is defined as two (2) consecutive plasma HIV-1 RNA levels of \geq 200 copies/mL. (2) Assigned dose refers to the dose allocated at the time of randomization/enrollment.

- Time to virologic failure at the assigned dose
- Proportion of participants moved to rescue arm or higher dose group

Note: Rescue is defined as subjects who were unable to maintain viral suppression, or experienced virologic failure, and moved to a higher dose of PRO 140

- Proportion of participants achieving viral re-suppression (HIV-1 RNA <50 copies/mL) during Treatment Phase after moving to rescue arm or higher dose group
- Time to achieving viral re-suppression (HIV-1 RNA <50 copies/mL) during Treatment Phase for subjects who moved to rescue arm or higher dose group

- Proportion of participants achieving viral re-suppression (HIV-1 RNA <50 copies/mL) after experiencing virologic failure (during the Treatment and Follow-up Phase)
- Time to achieving viral re-suppression (for virologic failure subjects) after re-initiation of oral combination antiretroviral regimen during the Follow-up Phase.
- Proportion of participants completing 24, 48 weeks of PRO 140 treatment with HIV-1 RNA <50 copies/mL
- Mean change in CD4 cell count, at each visit within the Treatment Phase
- To evaluate the prognostic factors of therapeutic success of PRO 140 monotherapy during the Treatment Phase.
 - CCR5 Receptor Occupancy
 - CCR5 Genotyping Status (heterozygotes or homozygotes)
 - gp120 genotyping
 - Baseline HIV-1 RNA Single Copy levels
 - Immune Activation Markers
 - PhenoSense® Entry Assay

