**Part 2 – Rescue Arm for Group A and Group B subjects**

- **Part 2 for Group A:** single arm, open-label treatment phase for Group A subjects electing to receive PRO 140 525mg SC after experiencing virologic failure on 350mg SC/weekly dose
- **Part 2 for Group B:** single arm, open-label treatment phase for Group B subjects electing to receive PRO 140 700mg SC after experiencing virologic failure on 525mg SC/weekly dose

**Note:** All ongoing subjects assigned to Group A receiving PRO 140 350mg SC weekly or assigned to Group B receiving PRO 140 525mg SC weekly have the option of participating in Part 2 should virologic failure occur.

The study is divided into three phases: Screening, Treatment and Follow-up.

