2.2 Design Overview

This study is a Phase 2b/3, multi-center, randomized, two-part, open-labeled study designed to evaluate safety and tolerability of the strategy of shifting clinically stable patients receiving suppressive combination antiretroviral therapy to PRO 140 monotherapy and maintaining viral suppression for 48 weeks following study entry.

Consenting patients will be shifted from combination antiretroviral regimen to weekly PRO 140 monotherapy for 48 weeks during the Treatment Phase with the one week overlap of existing retroviral regimen and PRO 140 at the beginning of the study treatment and also one week overlap at the end of the treatment in subjects who do not experience virologic failure. The first ~150 eligible subjects were enrolled to receive PRO 140 350mg SC weekly injection in a single-arm study. Subsequently, next ~150 subjects were randomized 1:1 to PRO 140 350mg (Group A) or PRO 140 525mg (Group B). An additional ~200 subjects will be randomized 1:1 to PRO 140 525mg (Group B) or PRO 140 700mg (Group C).

➤ **For the first ~150 enrolled subjects:**

- **Part 1:** 48-week, single-arm, open-label treatment phase
 - PRO 140 350mg SC weekly injection (Group A)

➤ **For the subsequent ~150 enrolled subjects:**

- **Part 1:** 48-week, randomized, two-arm, open-label treatment phase
 - PRO 140 350mg SC weekly injection (Group A)
 - PRO 140 525mg SC weekly injection (Group B)

➤ **For the subsequent ~200 enrolled subjects:**

- **Part 1:** 48-week, randomized, two-arm, open-label treatment phase
 - PRO 140 525mg SC weekly injection (Group B)
 - PRO 140 700mg SC weekly injection (Group C)

As noted below, subjects in Group A or Group B that experience virologic failure prior to week 48 in Part 1 have option of entering Part 2 wherein they receive higher dose of PRO 140 for remainder

of treatment phase or may re-initiate prior ART regimen (or an alternative regimen selected by their treating physician) at the discretion of the subject and Investigator.

Part 2 – Rescue Arm for Group A and Group B subjects

- **Part 2 for Group A:** single arm, open-label treatment phase for Group A subjects electing to receive PRO 140 525mg SC after experiencing virologic failure on 350mg SC/weekly dose
- **Part 2 for Group B:** single arm, open-label treatment phase for Group B subjects electing to receive PRO 140 700mg SC after experiencing virologic failure on 525mg SC/weekly dose

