Note: All ongoing subjects assigned to Group A receiving PRO 140 350mg SC weekly or assigned to Group B receiving PRO 140 525mg SC weekly have the option of participating in Part 2 should virologic failure occur.

The study will have three phases: Screening Phase, Treatment Phase and Follow-up Phase. More details are included in the protocol and Schedule of Assessments in Table 2-1, Table 2-2 and Table 2-3.

Table 2-1: Schedule of Assessments – Screening and Treatment Phase (T1 – T16)

Procedure/Assessments	Treatment Phase (T1 – T16)																In case of Treatment Failure	
	Visit SV	T1 (Pre-Rx) (Post-Rx) Within 6 weeks of SV	T2	T3	T4	T5	T6	T7	T8	T9	T10	T11	T12	T13	T14	T15		T16
Window Period	X																	
Informed Consent ^[1]	X																	
Eligibility Evaluation ^[2]	X																	
Pre-enrollment Eligibility	X	X																
Subject Demographics	X	X																
Medical History ^[3]	X	X ^[4]	X ^[4]	X ^[4]	X ^[4]	X ^[4]	X ^[4]	X ^[4]	X ^[4]	X ^[4]	X ^[4]	X ^[4]	X ^[4]	X ^[4]	X ^[4]	X ^[4]	X ^[4]	X ^[4]
Physical Examination	X	X ^[4]	X ^[4]	X ^[4]	X ^[4]	X ^[4]	X ^[4]	X ^[4]	X ^[4]	X ^[4]	X ^[4]	X ^[4]	X ^[4]	X ^[4]	X ^[4]	X ^[4]	X ^[4]	X ^[4]
Neurological Assessment ^[5]	X	X																
Vital Signs ^[6]	X	X	X	X	X	X	X	X	X	X	X	X	X	X	X	X	X	X
Body Weight & Height	X																	
ECG	X																	
Complete Blood Count (CBC) ^[7]	X											X	X	X	X	X	X	X
Biochemistry ^[8]	X											X	X	X	X	X	X	X
Coagulation Indices	X											X	X	X	X	X	X	X
Serum Pregnancy Test ^[9]	X											X	X	X	X	X	X	X
Urinalysis ^[10]	X											X	X	X	X	X	X	X
Urine Pregnancy Test ^[9]	X											X	X	X	X	X	X	X
HBsAg	X																	
Plasma HIV-1 RNA level	X											X	X	X	X	X	X	X
TruCount T assay ^[11]	X											X	X	X	X	X	X	X
Trofile® DNA Assay	X											X	X	X	X	X	X	X
Trofile® RNA Assay																		
HIV-1 Drug Resistance Assay ^[12]	X											X	X	X	X	X	X	X
Serum concentration of ART drugs ^[13]												X	X	X	X	X	X	X
Randomization (via CTMS) ^[29]																		
PRO 140 Administration ^[30]																		
- Group A (350mg SC)		X	X	X	X	X	X	X	X	X	X	X	X	X	X	X	X	X
- Group B (525mg SC)																		
- Group C (700mg SC)																		
Combination ART Regimen ^[14]	X	X	X	X	X	X	X	X	X	X	X	X	X	X	X	X	X	X
Injection Site Reaction Assessment ^[15]			X	X	X	X	X	X	X	X	X	X	X	X	X	X	X	X
Injection Site Pain Assessment																		

Procedure/Assessments	Treatment Phase (T1 – T16)																In case of Treatment Failure		

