- [21] immune activation markers (CRP, IL-6, D-Dimer)
- [22] Monogram Biosciences HIV-1 PhenoSense® Entry assay with AMD3100 (X4 inhibitor drug), Maraviroc and PRO 140 (R5 inhibitor drugs). Sample collected for Trofile DNA/RNA at Screening will be used to test PhenoSense® Entry for eligible/enrolled subjects at Baseline.
- [23] Flow cytometry and the 2D7 MAb will be used to measure CCR5 expression levels on peripheral blood mononuclear cells (PBMCs)
- [24] Quest Diagnostics HIV-1 Coreceptor Tropism with Reflex to Ultradeep Sequencing or HIV-1 Proviral Tropism.
- [25] If assessment **not** performed at SV.
- [26] To evaluate PRO 140 concentration and HIV-1 RNA level in cerebrospinal fluid (CSF)
- [27] To evaluate PRO 140 concentration and HIV-1 RNA level in genital secretions
- [28] Monogram Biosciences Trofile® DNA or RNA assay (or both) will be performed at the Virologic Failure Visit depending on the last known HIV-1 RNA levels.
- [29] Randomization will occur via CTMS
- [30] Should VF occur, Group A or Group B subjects may transition to high dose IP and continue in 48-week treatment phase.
- [31] To assess the number CCR5 receptors on patients’ CD4 cell surface, and number and percentage of CCR5 receptors that are covered by PRO 140. Sites should not collect samples on Fridays, since InCellDx lab cannot receive samples on Saturdays.
- [32] No new sample collection needed. The residual whole blood sample collected for tropism assessment at Screening or at post-treatment visits will be used for testing of CCR5 genotyping (homozygous or heterozygous status).

Table 2-2: Schedule of Assessments –Treatment Phase (T17 – T48)

Procedure/Assessments	Treatment Phase (T17 – T48)											In case of Treatment Failure	
	T17	T18-21	T22-25	T26-29	T30-33 ±3 days since last treatment	T34-37	T38-41	T42-45	T46	T47	T48		VF
Visit													
Window Period													
Physical Examination	X ^[1]	X ^[1]	X ^[1]	X ^[1]	X ^[1]	X ^[1]	X ^[1]	X ^[1]	X ^[1]	X ^[1]	X	X	X
Neurological Assessment ^[2]													X
Vital Signs ^[3]	X	X	X	X	X	X	X	X	X	X	X	X	X
ECG													X
Complete Blood Count (CBC) ^[4]			X		X						X	X	X
Biochemistry ^[5]			X		X						X	X	X
Coagulation Indices			X		X						X	X	X
Urinalysis			X		X						X	X	X
Plasma HIV-1 RNA level ^[6]	X	X	X	X	X	X	X	X	X	X	X	X	X
TruCount T assay ^[7]	X	X	X	X	X	X	X	X	X	X	X	X	X
Trofile® DNA Assay													X ^[20]
Trofile® RNA Assay													X ^[20]
HIV-1 Drug Resistance Assay ^[8]													X

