7.5.4 Virologic Failure

Virologic failure is defined as two (2) consecutive plasma HIV-1 RNA levels of ≥ 200 copies/mL.

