7.5.6 Viral Re-suppression

For all subjects with virologic failure, viral re-suppression is defined as having a plasma HIV-1 RNA levels of <50 copies/mL after experiencing virologic failure.

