8.2.2.3 Proportion of participants moved to rescue arm or higher dose group

The percentages of subjects moved to a rescue arm or higher dose will be presented descriptively by treatment groups for the ITT and PP populations.

Note: Rescue is defined as subjects who were unable to maintain viral suppression, or experienced virologic failure, and moved to a higher dose of PRO 140.

8.2.2.4 Proportion of participants achieving viral re-suppression (HIV-1 RNA <50 copies/mL) during Treatment Phase after moving to rescue arm or higher dose group

The percentages of subjects with virologic re-suppression (as defined in [Section 7.5.8](#)) will be presented descriptively by treatment groups for the subset of the ITT and PP populations that moved to a rescue arm or higher dose group.

8.2.2.5 Time to achieving viral re-suppression (HIV-1 RNA <50 copies/mL) during Treatment Phase for subjects who moved to rescue arm or higher dose group

The number of observations, mean, standard deviation, median, and minimum and maximum values will be presented to summarize time to viral re-suppression (as defined in [Section 7.5.9](#)) by treatment groups for the subset of the ITT and PP populations that moved to a rescue arm or higher dose group.

8.2.2.6 Proportion of participants achieving viral re-suppression (HIV-1 RNA <50 copies/mL) after experiencing virologic failure (during the Treatment and Follow-up Phase)

The percentages of subjects with virologic re-suppression (as defined in [Section 7.5.8](#)) will be presented descriptively by treatment groups for the subset of the ITT and PP populations that experienced virologic failure.

8.2.2.7 Time to achieving viral re-suppression (for virologic failure subjects) after re-initiation of oral combination antiretroviral regimen during the Follow-up Phase.

The number of observations, mean, standard deviation, median, and minimum and maximum values will be presented to summarize time to viral re-suppression after re-initiation of oral combination antiretroviral regimen (as defined in [Section 7.5.10](#)) by treatment groups for the subset of the ITT and PP populations that experienced virologic failure and had re-initiation of oral combination antiviral therapy.

8.2.2.8 Proportion of participants completing 24, 48 weeks of PRO 140 treatment with HIV-1 RNA <50 copies/mL

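### The Rescue note covers dose increases without confirmed virologic failure, the Part 2 entry text does not, and the SAP has no workable rule for such a subject

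*SAP*

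**What the plan says.** **Rescue.** SAP 3.1.2 defines the group as "subjects who were unable to maintain viral suppression, or experienced virologic failure, and moved to a higher dose of PRO 140". SAP 8.2.2.3, the Protocol synopsis and Protocol 8.2.2 carry the same note. Its first limb has no threshold.

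**Failure.** SAP 7.5.4: "Virologic failure is defined as two (2) consecutive plasma HIV-1 RNA levels of" at least 200 copies/mL.

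**Entry to Part 2.** SAP 2.2 says that "subjects in Group A or Group B that experience virologic failure prior to week 48 in Part 1 have option of entering Part 2", and that ongoing Group A and B subjects "have the option of participating in Part 2 should virologic failure occur". Protocol Section 3 describes the Group B rescue arm as for "Group B subjects electing to receive PRO 140 700mg SC after experiencing virologic failure on 525mg SC/weekly dose". Footnote 30 to SAP Table 2-1 reads: "Should VF occur, Group A or Group B subjects may transition to high dose IP and continue in 48-week treatment phase". Protocol 4.2, 4.3 and 5.2.1 set the same condition.

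**Re-suppression.** SAP 7.5.6 begins "For all subjects with virologic failure, viral re-suppression is defined as having a plasma HIV-1 RNA levels" and requires a value below 50 copies/mL after failure. SAP 7.5.7 counts days from the failure date. The rescue outcomes in 8.2.2.4 and 8.2.2.5, however, analyse everyone moved to the rescue arm or a higher dose, with no condition on prior failure.

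**Time to failure.** Under SAP 7.5.5, a subject without failure is followed to the last visit or early termination. A dose increase does not end the count. SAP 7.3 plans no imputation.

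**The concern.** The note describes people whom the entry text does not admit, and the analysis rules do not say what to do with them. The outcomes affected are listed as primary efficacy measures. A subject moved up before failure was confirmed would count as not having failed at a dose that he or she was no longer taking. The distortion would run one way: Groups A and B can be moved up, whereas Group C has no higher dose in the plan. It could therefore flatter the lower doses in the by-group description. The study is open label, so any such move would be made knowing both dose and viral load.

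Part of the problem remains even if nobody was moved early. The outcome in 8.2.2.5 concerns re-suppression on the higher dose, but the only available clock starts at failure rather than at the move.

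**Working it through.** The documents give no event rate, power or count of early moves, so there is no planned figure on this point to reproduce beyond the group sizes.

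**1. Group sizes** (SAP Section 5; Protocol Section 3 agrees).
- A = 150 + 75 = 225
- B = 75 + 100 = 175
- C = 100
- Total = 500, which matches SAP Section 4, as does the 100 on 700 mg.

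Protocol Section 4 describes the first 300 as all randomised between A and B. The SAP allocation is used here.

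**2. Tracing one subject moved up without two consecutive values of at least 200 copies/mL, and with no later VF.**

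| SAP section | Result as written |
|---|---|
| 8.2.2.3 moved to rescue | Counted |
| 8.2.2.1 VF at assigned dose | In the denominator, not the numerator |
| 7.5.5 and 8.2.2.2 time to VF | Runs to last visit or early termination, including time on the higher dose |
| 8.2.2.4 re-suppression after rescue | In the denominator; 7.5.6 requires a prior failure |
| 8.2.2.5 time to re-suppression | In the analysis set; 7.5.7 supplies no start date |
| 8.2.2.6 re-suppression after VF | Outside the analysis set |

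**3. Effect on the VF proportion.** With k such subjects among N, the proportion is lower by 100 × k/N points than if they were counted as failures. The values of k are assumptions.

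| k | Group A, N about 225 | Group B, N about 175 |
|---|---|---|
| 0 | 0 | 0 |
| 1 | 0.44 | 0.57 |
| 5 | 2.2 | 2.9 |
| 10 | 4.4 | 5.7 |

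**4. Effect on re-suppression after rescue.** Assume R = 50 rescued, of whom a share s = 70% reach below 50 copies/mL, equally among early movers and others. Counting everyone gives 70%. Applying 7.5.6 literally gives s × (R − k)/R:
- k = 0: 70%
- k = 5: 0.70 × 45/50 = 63%
- k = 10: 0.70 × 40/50 = 56%

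**5. Section references.** SAP 8.2.2.4 cites 7.5.8, which is time to re-suppression after restarting antiretroviral therapy (ART). SAP 8.2.2.5 cites 7.5.9, which does not exist. Elsewhere, 8.2.2.1 cites 7.5.6 for VF (actually 7.5.4) and 8.2.2.2 cites 7.5.7 for time to VF (actually 7.5.5). The references thus run two too high, so 7.5.6 and 7.5.7 are the likely targets. Section 7.5.8 is also limited to subjects with failure, so the gap remains on either reading.

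**The case against.** The strongest reply is that the affected group is empty. Every operative statement makes VF the condition for a higher dose. The Rescue note is only a gloss on an outcome measure and admits nobody, and its first limb may be a loose paraphrase of failure. This stands to the extent that the documents do not show any early move, so the count effects start at zero. A reader might infer that subjects have been lost from the VF numerator, or apply an assumed rescue rate to obtain a firm percentage. The documents support neither, since they give no rescue rate and no share moved early.

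A reader might also infer that early movers can never count as re-suppressed. That is too absolute. The outcome title asks only for a value below 50 copies/mL after the move, which would count them. A subject who later fails on the higher dose and then falls below 50 also meets 7.5.6. The accurate statement is that the SAP conflicts with itself.

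Further, early movers would be visible elsewhere. The proportion rescued is reported by group, and completion of 24 and 48 weeks below 50 copies/mL is reported at the assigned dose. No inference is planned (SAP 7.3, 7.4). These points limit the consequence, but they do not supply the missing rules.

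Finally, counting every dose increase as a primary failure would turn the protocol's virologic endpoint into a composite. That objection is sound, and such a change is not proposed as the primary analysis.

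**Conclusion.** The inconsistency is real and should be resolved. Its numerical effect on the VF proportion is conditional: about 0.44 points per subject in Group A and 0.57 in Group B, on the SAP's planned group sizes and provided the subject is not otherwise counted as a failure. It is nil in Group C, and nil everywhere if entry was strictly limited to VF. The documents do not allow a total to be stated.

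One defect does not depend on early moves. The rescue outcomes have wrong section references, and their clock starts at failure although the outcome concerns response after the dose increase. Nothing here decides which entry condition for rescue is right.

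**What to change.** 1. Reconcile the Rescue note (SAP 3.1.2 and 8.2.2.3; Protocol synopsis and 8.2.2) with the Part 2 entry text. The sponsor decides which condition applies.
2. For SAP 8.2.2.4 and 8.2.2.5, define re-suppression as HIV-1 RNA below 50 copies/mL after the dose increase, with the clock starting on the date of the increase. This parallels 7.5.8, which already counts from the restart of ART. Correct the references to 7.5.8 and 7.5.9.
3. In SAP 7.5.5 and 8.2.2.1–8.2.2.2, state that time after a dose increase is not failure-free time at the assigned dose. Report by group the number moved up without confirmed failure, including zero. Add a sensitivity summary that counts them as failures at the switch date, and keep the protocol's VF definition as primary.

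The cost is SAP wording, alignment of the protocol note, and one extra summary. The assigned-dose figure may look slightly less favourable. For rescued subjects with confirmed VF, the clock in 8.2.2.5 would start at the move rather than at failure; this should be stated openly as a change.
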